### ADVERSE REACTIONS

- Reactions may occur in patients who are hypersensitive to cyanoacrylate or formaldehyde. See CONTRAINDICATIONS.
- Adverse reactions may be experienced following contact with the eye.

### DIRECTIONS FOR USE

1. The application of DERMABOND ADVANCED™ Adhesive requires thorough wound cleansing. Follow standard surgical practice for wound preparation before application of DERMABOND ADVANCED™ Adhesive (i.e., anesthetize, irrigate, debride, assure hemostasis, and close deep layers making sure that the wound edges can be easily approximated).
2. Pat the wound dry with dry, sterile gauze to assure direct contact of the DERMABOND ADVANCED™ Adhesive to the skin. Moisture accelerates DERMABOND ADVANCED™ Adhesive's polymerization and may affect wound closure results.
3. To prevent inadvertent flow of liquid DERMABOND ADVANCED™ Adhesive to unintended areas of the body, the wound should be maintained in a horizontal position and the DERMABOND ADVANCED™ Adhesive should be applied from above the wound.
4. DERMABOND ADVANCED™ Adhesive should be used immediately after crushing the ampoule, since the liquid DERMABOND ADVANCED™ Adhesive will flow freely from the tip for only a few minutes.
5. Refer to the instructions on the package for crushing the ampoule and expressing the liquid adhesive. Remove the applicator from the blister package. Hold the applicator with the thumb and a finger, away from the patient to prevent any unintentional placement of the liquid DERMABOND ADVANCED™ Adhesive into the wound or on the patient. With the applicator tip pointing downward, apply pressure at the midpoint of the bulb to crush the ampoule. Gently squeeze the applicator sufficiently to moisten the internal filter with the liquid adhesive. Stop squeezing and allow the liquid DERMABOND ADVANCED™ Adhesive to draw back into the applicator.
6. Approximate the wound edges with gloved fingers or sterile forceps. Slowly apply the liquid DERMABOND ADVANCED™ Adhesive in one continuous layer to the surface of the approximated wound edges using a gentle brushing motion. Maintain manual approximation of the wound edges for approximately 60 seconds after the application. The width of the layer can be increased or decreased by adjusting the amount of pressure applied to the bulb during application. Full apposition strength is expected to be achieved within minutes after the adhesive is applied. Full polymerization is expected when the DERMABOND ADVANCED™ Adhesive layer is no longer sticky.
7. Do not apply liquid or ointment medications onto wounds closed with DERMABOND ADVANCED™ Adhesive because these substances can weaken the polymerized film, leading to skin edge separation.
8. Protective dry dressings such as gauze may be applied only after DERMABOND ADVANCED™ Adhesive film is completely polymerized: not tacky to the touch after a few minutes. Allow the DERMABOND ADVANCED™ Adhesive to fully polymerize before applying a bandage.

9. Patients should be instructed to not pick at the polymerized film of DERMABOND ADVANCED™ Adhesive. Picking at the film can disrupt its adhesion to the skin and cause skin edge separation.
10. Patients should be instructed that until the polymerized film of DERMABOND ADVANCED™ Adhesive has sloughed naturally (usually in 5–10 days), there should be only transient wetting of the treatment site. Patients may immediately shower or bathe the site gently as directed by their physician. The site should not be scrubbed, soaked, or exposed to prolonged wetness until after the film has sloughed naturally and the physician has determined that the wound is adequately healed. Patients should be instructed not to swim during this period.
11. If removal of DERMABOND ADVANCED™ Adhesive is necessary for any reason, carefully apply petroleum jelly or acetone to the DERMABOND ADVANCED™ Adhesive film to help loosen the bond. Peel off the film; do not pull the skin edges apart.

#### HOW SUPPLIED

DERMABOND ADVANCED™ Adhesive is supplied sterile, in a pre-filled, single-use applicator. The pen style applicator consists of a crushable ampoule contained within a plastic applicator. The applicator contains the liquid adhesive. The applicator is supplied in a blister package to maintain the sterility of the device until opened or damaged. DERMABOND ADVANCED™ Adhesive is available in boxes of 6 or 12 applicators.

#### STORAGE

Recommended storage conditions: below 30°C, 86°F, away from moisture, direct heat, and direct light. Do not use after expiry date.

[figure not shown]
#### STERILITY

DERMABOND ADVANCED™ Adhesive has been sterilized by dry heat and ethylene oxide gas. Do not resterilize. Do not use if package is opened or damaged. Discard any unused material following completion of each medical procedure.

#### STERILE SINGLE USE ONLY

#### REPORTING

Physicians should use the following toll-free number [name] (valid in U.S.A. only), when reporting adverse reactions or potentially threatening complications involving DERMABOND ADVANCED™ Adhesive.

PM72434B  
LAB0012189.2  
STATUS: 03/2011

ETHICON, LLC  
San Lorenzo, Puerto Rico 00754  
© ETHICON, Inc. 2011

[figure not shown]

### 15.3 Patient and Observer Scar Assessment Scale

## POSAS Patient scale

The Patient and Observer Scar Assessment Scale v2.0 / EN

Date of examination: _____	Name of patient: _____
Observer: _____	_____
Location: _____	Date of birth: _____
Research / study: _____	Identification number: _____

	1 = no, not at all	yes, very much = 10
	 1  2  3  4  5  6  7  8  9  10	
HAS THE SCAR BEEN PAINFUL THE PAST FEW WEEKS?		
HAS THE SCAR BEEN ITCHING THE PAST FEW WEEKS?		
	1 = no, as normal skin	yes, very different = 10
IS THE SCAR COLOR DIFFERENT FROM THE COLOR OF YOUR NORMAL SKIN AT PRESENT?		
IS THE STIFFNESS OF THE SCAR DIFFERENT FROM YOUR NORMAL SKIN AT PRESENT?		
IS THE THICKNESS OF THE SCAR DIFFERENT FROM YOUR NORMAL SKIN AT PRESENT?		
IS THE SCAR MORE IRREGULAR THAN YOUR NORMAL SKIN AT PRESENT?		
	1 = as normal skin	very different = 10
WHAT IS YOUR OVERALL OPINION OF THE SCAR COMPARED TO NORMAL SKIN?	 1  2  3  4  5  6  7  8  9  10	

# POSAS Observer scale

The Patient and Observer Scar Assessment Scale v2.0 / EN

Date of examination: \_\_\_\_\_

Observer: \_\_\_\_\_

[figure not shown]
Location: \_\_\_\_\_

Research / study: \_\_\_\_\_

Name of patient: \_\_\_\_\_

Date of birth: \_\_\_\_\_

Identification number: \_\_\_\_\_

PARAMETER	1 = normal skin      worst scar imaginable = 10										CATEGORY
	1	2	3	4	5	6	7	8	9	10	
VASCULARITY											PALE   PINK   RED   PURPLE   MIX
PIGMENTATION											HYPO   HYPER   MIX
THICKNESS											THICKER   THINNER
RELIEF											MORE   LESS   MIX
PLIABILITY											SUPPLE   STIFF   MIX
SURFACE AREA											EXPANSION   CONTRACTION   MIX
OVERALL OPINION											

## Explanation

The observer scale of the POSAS consists of six items (vascularity, pigmentation, thickness, relief, pliability and surface area). All items are scored on a scale ranging from 1 ('like normal skin') to 10 ('worst scar imaginable'). The sum of the six items results in a total score of the POSAS observer scale. Categories boxes are added for each item. Furthermore, an overall opinion is scored on a scale ranging from 1 to 10. All parameters should preferably be compared to normal skin on a comparable anatomic location.

## Explanatory notes on the items:

- **VASCULARITY** Presence of vessels in scar tissue assessed by the amount of redness, tested by the amount of blood return after blanching with a piece of Plexiglas
- **PIGMENTATION** Brownish coloration of the scar by pigment (melanin); apply Plexiglas to the skin with moderate pressure to eliminate the effect of vascularity
- **THICKNESS** Average distance between the subcuticular-dermal border and the epidermal surface of the scar
- **RELIEF** The extent to which surface irregularities are present (preferably compared with adjacent normal skin)
- **PLIABILITY** Suppleness of the scar tested by wrinkling the scar between the thumb and index finger
- **SURFACE AREA** Surface area of the scar in relation to the original wound area

COPYRIGHT © P.P.M. VAN ZUIJLEN, BEVERWIJK-NL

---

## 15.4 Modified Hollander Cosmesis Scale

### Modified Hollander Cosmesis Scale (part of the “Wound registry”)

Evaluation Characteristics	Yes (poor)	No (good)
Step-off borders	1	0
Contour irregularities	1	0
Wound margin separation	1	0
Edge inversion	1	0
Excessive inflammation	1	0
Overall appearance	1	0

### 15.5 Product-related Questionnaire for Investigators

Each investigator will complete this questionnaire after the assumed last randomized subject at the site has completed the Month 1 or Early Discontinuation (if earlier than Month 1) visit (one per site).

Date of completion: dd/mmm/YYYY

1)	The instructions for use were:	MAR-CUTIS		Dermabond	
	Clear and easy to understand for you	Yes	No	Yes	No
	Clear and easy to implement for subjects	Yes	No	Yes	No

if answered “No” for MAR-CUTIS, please explain the issue below:

if answered “No” for Dermabond, please explain the issue below:

2)	Package opening, assembly and preparation of the syringe was:	MAR-CUTIS		Dermabond	
	Easy	Yes	No	Yes	No
	Fast	Yes	No	Yes	No

if answered “No” for MAR-CUTIS, please explain the issue below:

if answered “No” for Dermabond, please explain the issue below:

3)	Preparation of the target wound area was easy?	MAR-CUTIS		Dermabond	
		Yes	No	Yes	No
		Yes	No	Yes	No

if answered “No” for MAR-CUTIS, please explain the reason below:

if answered “No” for Dermabond, please explain the reason below:

4)	Appropriate thickness of the strip was easy to assess?	MAR-CUTIS		Dermabond	
		Yes	No	Yes	No
		Yes	No	Yes	No

if answered "No" for MAR-CUTIS, please explain the issue below:

if answered "No" for Dermabond, please explain the issue below:

5)	Maintaining the target wound edges during application was easy:	MAR-CUTIS		Dermabond	
		Yes	No	Yes	No
		Yes	No	Yes	No

if answered "No" for MAR-CUTIS, please explain the issue below:

if answered "No" for Dermabond, please explain the issue below:

6)	Precision of application was satisfactory?	MAR-CUTIS		Dermabond	
		Yes	No	Yes	No
		Yes	No	Yes	No

if answered "No" for MAR-CUTIS, please explain the reason below:

if answered "No" for Dermabond, please explain the reason below:

7)	Time for the glue to harden was:	MAR-CUTIS	Dermabond
		Too quick	Too quick
		Too slow	Too slow
		Just right	Just right

If you have any comments, please provide below:

8)	Do you have previous experience with other topical skin adhesive?	yes	no
----	---	-----	----

If answered "yes",

	Was MAR-CUTIS easier to apply than the other topical skin adhesives?	yes	no
	Was Dermabond easier to apply than the other topical skin adhesives?	yes	no

9)	Overall, the use of the glue made wound closure more hassle-free for me than using sutures	MAR-CUTIS	Dermabond		
		Yes	No	Yes	No

if answered "no" for MAR-CUTIS, please explain the reason below:

if answered "no" for Dermabond, please explain the reason below:

---

## 15.6 Subject-related Questionnaire for Investigators

### Subject-related Questionnaire for investigators

Please complete this questionnaire for each subject in the study at specified time points.

#### Section 1 (to be completed at Day 0)

- |  |     |    |
|--|-----|----|
| 1) Application of the glue strip   |     |    |
| Easy   | Yes | No |
| Fast   | Yes | No |
| Without complications  | Yes | No |
| 2) Overall, would you say that the use of the glue saved you time as compared with the use of sutures? | Yes | No |
| 3) Overall, would you say that the use of the glue reduced effort?                                     | Yes | No |

#### Section 2 (to be completed at Month 1)

##### Practical experience

- 8) Please rate your impression on the usability of this product on a scale from 1 (poor = very difficult to use) to 100 (excellent = very easy to use)

- 9) With regards to this subject, my experience with MAR-CUTIS can be described as
- Very satisfied
  - Satisfied
  - Dissatisfied
  - Very dissatisfied
- 10) Did you observe any pain or burning at time of application?
- Yes
  - No

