
 
To compare the wound infection incidence between both treatment groups.
 
	
 
Wound infection incidence assessed at the Day 10, Month 1, and Month 3 visits or at the Early Discontinuation visit (diagnosed according to the Centers for Disease Control and Prevention [CDC] criteria for surgical site infection [Section 15.1]).
 
Wound infection assessed on a binary scale (“1 - yes” or “0 - no”) for the following criteria: 
 
Presence of erythema
 
Presence of edema
 
Presence of pain at rest
 
Presence of elevated temperature
 
 A total score will be calculated for each subject.
 

 
To evaluate the investigator satisfaction with the cosmetic outcome after the closure of the target surgical incision/laceration with MAR-CUTIS versus Dermabond Advanced.
 
	
 
Investigator-completed POSAS done at the Month 1 and Month 3 visits or at the Early Discontinuation visit (if Early Discontinuation occurs before Month 1).
 

	

Investigator-completed Modified Hollander Cosmesis Scale (mHCS) done at the Day 10 and Month 1 visits or at the Early Discontinuation visit (if Early Discontinuation occurs before Month 1).

To evaluate the subject comfort with the device during and after treatment with MAR-CUTIS versus Dermabond Advanced.

	

A questionnaire related to subject experience and satisfaction with the device completed by the subject at the Day 10 and Month 1 visits or at the Early Discontinuation visit (if Early Discontinuation occurs before Month 1).

A subject-related questionnaire completed by the investigator at the Day 0 and Month 1 visits or at the Early Discontinuation visit (if Early Discontinuation occurs before Month 1).

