### 7.4.4 Method of Assigning Subjects to Treatment Groups

Subjects (ie, the unique subject identifier [ID] consisting of center ID and subject ID) will be randomly allocated to treatment according to a randomization scheme designed using the covariate-adjusted dynamic allocation method as implemented in Balance (Medidata, 2015). The algorithm combines complete randomness with a minimization method (Pocock and Simon, 1975), not only looking at marginal balances, but also considering the treatment balances overall and within individual strata, to ensure a balanced treatment allocation. Based on the expected clinical relevance of the explanatory variables for incision and laceration closure, the algorithm is implemented by assigning a different weight to the stratification factors to be included in the trial and minimize unbalances (ie, wound type having more importance than the other 2 factors, and age group having more importance than skin type). Further details regarding the parameters used to implement the randomization in balance are documented in the form “Balance Study Configuration Requirements”.

The incision/laceration will be prepared for closure as per the standard of care at a treating hospital. The investigator will assess the need and perform closure of deep tissue layers as necessary before proceeding with the randomization and subsequently with the closure of the last (dermal) layer with the IMD.

Eligible subjects will be randomized 2:1 to MAR-CUTIS or Dermabond Advanced.

The study will include 3 levels of stratification as randomization factors:

- By wound type (lacerations and incisions).
- By skin type according to the Fitzpatrick classification (types I to III versus types IV to VI).
- By age group (aged 2 to 21 years and  $\geq 22$  years).

The primary efficacy analysis will consider the stratification factors as explanatory variables in the model. Additionally, center will be considered as a further randomization factor as recommended by International Council for Harmonisation (ICH) E9.

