### 9.2 Satisfaction Questionnaires

- Patient and Observer Scar Assessment Scale (Section 15.3) will be completed by the subject and investigator at the Month 1 and Month 3 visits or the Early Discontinuation visit (Section 7.1.2).
  - The POSAS is a questionnaire that was developed to assess scar quality. It consists of 2 separate 6-item scales (Observer Scale and Patient Scale), both of which are scored on a 10-point rating scale.
  - Each scale has an overall “opinion” with 1 being no pain, no itching, or normal skin and 10 being worst scar imaginable with pain and itching.
- Modified Hollander Cosmesis Scale (Section 15.4) is completed by investigator at the Day 10, Month 1, and Early Discontinuation (if earlier than Month 1 or if the questionnaire has not previously been completed) visits (Section 7.1.2).
  - The mHCS consists of 6 wound characteristics, evaluated as “poor” or “good”

- 
- Each of the characteristics is graded on a 0 (no/good) or 1 (yes/poor) point scale. A total cosmetic score is derived by the addition of the scores.
  - One product-related questionnaire for investigators (Section 15.5) will be completed for each site when the last randomized subject at the site completes the Month 1 visit (Section 7.1.2). This questionnaire will be completed at the Early Discontinuation visit if the visit is earlier than the Month 1 visit or if the questionnaire has not previously been completed.
    - This questionnaire consists of 8 yes/no questions and 1 opinion question that evaluate the investigator's experience with use of the adhesive (ie, instructions easy to understand, preparation of the syringe being easy and fast, glue hardening time).
  - Subject-related questionnaire completed by investigators (Section 15.6) will be done at the Day 0, Month 1, and Early Discontinuation (if earlier than Month 1 or if the questionnaire has not previously been completed) visits and if there is premature removal of the adhesive (Section 7.1.2).
    - This questionnaire consists of 5 yes/no questions that assess the investigator's experience applying the adhesive (ie, easy to use, fast, without complications), a visual analog scale that rates usability of the product from 1 to 100, and 1 question that evaluates satisfaction with the adhesive. The questions are categorized into 3 sections, each section to be completed at different visits.

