#### **10.1.3.2 Definition and Analysis of Secondary Efficacy Endpoints**

Secondary efficacy endpoints, as described in Section 6 are:

- Comparison of the dehiscence rate between MAR-CUTIS and Dermabond Advanced at the Month 1 or Early Discontinuation visit.

- 
- Score from POSAS recorded for the subject at Month 1 and Month 3/Early Discontinuation.
  - Comparison of wound infection incidence assessed on a binary scale ('1=yes' or '0=no') between both treatment groups. In addition, a total score will be calculated for each subject based on the wound infection assessed on the presence of erythema, edema, pain or elevated temperature (also assessed on a binary scale: "1=yes" or "0=no" for each characteristic).
  - Score from POSAS recorded for the investigator at Month 1 and Month 3/Early Discontinuation. Assessments will be presented by subject treated.
  - Score from mHCS recorded for the investigator at Day 10 and Month 1 or Early Discontinuation. Assessments will be presented by subject treated.
  - Score from a questionnaire related to subject experience and satisfaction with the device at Day 10 and at Month 1 or Early Discontinuation.
  - Scores from 2 investigator-completed questionnaires to evaluate overall satisfaction and ease of use with the device:
    - A product-related questionnaire to be completed for each center when the last randomized subject at the center completes the Month 1 visit or at Early Discontinuation. This assessment will be presented by center.
    - A subject-related questionnaire at Day 0 and Month 1 or Early Discontinuation. This assessment will be presented by subject treated.

Secondary efficacy endpoints will be summarized using descriptive statistics.

FAS will be used on all analyses.

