13.2.6 Medical practitioner overall satisfaction and ease of use with the Device

For the evaluation of the overall satisfaction of the medical practitioner with the Device during and after the closure of the target surgical incision/laceration two questionnaires will be applied:

- 1) Product-related questionnaire for Investigators, to be completed for each center when the last randomized subject at the center completes the D10 visit. The same questionnaire will be completed for both MAR-CUTIS and Dermabond.

This questionnaire consists of 8 yes/no questions and 1 opinion question that evaluate the investigator's experience with use of the adhesive (i.e., instructions easy to understand, preparation of the syringe being easy and fast, glue hardening time).

- 2) Subject-related questionnaire for Investigators, to be completed at the Day 0 and Month 1 visits, and recorded in the e-CRF.
 - The questionnaire for Day 0 consists of 5 yes/no questions that assess the investigator's experience applying the adhesive (i.e., easy to use, fast, without complications, time saving and reduced efforts).
 - The questionnaire for Month 1 consists of a visual analog scale that rates usability of the product from 1 to 100, and two questions that evaluate the experience with the adhesive and the pain or burning at the time of application. Moreover, it also contains additional questions to describe the event of a premature removal of the adhesive.

Descriptive statistics for each question of both questionnaires will be presented for the analysis of this endpoint.

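### Month 1 item 9 of the investigator's subject-related questionnaire names MAR-CUTIS only, so Dermabond-arm answers to this one descriptive satisfaction item would be ambiguous

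*Protocol*

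**What the plan says.** Protocol Section 15.6 opens with the instruction "Please complete this questionnaire for each subject in the study at specified time points", so the form applies to both arms. Protocol Section 7.4.4 states that "Eligible subjects will be randomized 2:1 to MAR-CUTIS or Dermabond Advanced".

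In the part of the form completed at Month 1, item 9 reads "With regards to this subject, my experience with MAR-CUTIS can be described as" and offers four answers, from very satisfied to very dissatisfied. There is no Dermabond version and no not-applicable box.

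The text that describes the form is neutral about the product. Protocol Section 9.2 counts "1 question that evaluates satisfaction with the adhesive". SAP Section 13.2.6 says the Month 1 part includes "two questions that evaluate the experience with the adhesive and the pain or burning at the time of application".

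The form serves comparative and satisfaction endpoints. Protocol Section 6 places it under the objective on subject "comfort with the device during and after treatment with MAR-CUTIS versus Dermabond Advanced". Protocol Section 10.1.3.2 lists it again under "Scores from 2 investigator-completed questionnaires to evaluate overall satisfaction and ease of use with the device", with the specification "A subject-related questionnaire at Day 0 and Month 1 or Early Discontinuation. This assessment will be presented by subject treated". SAP Section 13.2.6 calls for descriptive statistics on each question, and SAP Section 8.1 has all presentations split by arm, with an overall column.

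**The concern.** For a Dermabond subject, item 9 asks the investigator to rate a product that this subject did not receive. The investigator can skip it, answer for the glue that was used, or give a general view of MAR-CUTIS formed on other subjects. Nothing on the form records which was done.

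Under the SAP's display rules a Dermabond column for this item will be produced all the same. A reader who goes by the SAP's description would take that column as satisfaction with Dermabond, and would compare it with the MAR-CUTIS column. The overall column would mix the two kinds of answer.

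What is at stake is the one rating on this form that addresses investigator satisfaction directly, in an open-label trial whose satisfaction endpoints are meant to set the two products side by side.

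**Working it through.** No stated result depends on this item, so the check is mainly a comparison of wording.

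**Step 1: how many subjects are affected.** Inputs are 189 treated subjects and 2:1 allocation (Protocol Sections 7.3.1 and 7.4.4).

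- MAR-CUTIS: 189 × 2/3 = 126
- Dermabond Advanced: 189 × 1/3 = 63

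Both match the planned arm sizes in Protocol Section 10.2. With full follow-up, item 9 would be put for about 63 subjects who did not receive the product it names, that is 63/189 = one third of the overall column. The 126 MAR-CUTIS subjects are unaffected. The count assumes that every Dermabond subject reaches Month 1 or has an earlier discontinuation visit.

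**Step 2: which items on the form name a product.**

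| Part of form 15.6 | Content | Product named? |
|---|---|---|
| Day 0, question 1 | application easy, fast, uncomplicated | No (glue strip) |
| Day 0, questions 2 and 3 | time saved, effort reduced | No (the glue) |
| Month 1, item 8 | usability, 1 to 100 | No (this product) |
| Month 1, item 9 | satisfaction, four levels | **Yes, MAR-CUTIS only** |
| Month 1, item 10 | pain or burning at application | No |

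Item 9 is the only one of these that names a device.

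**Step 3: form against description.** Protocol Section 9.2 and SAP Section 13.2.6 both describe the item in terms of the adhesive, whichever was used. The printed item does not match either description.

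**Step 4: how the same issue is handled elsewhere.** The subject-completed questionnaire (Section 15.7) has one MAR-CUTIS-specific question, on transparency, and gives Dermabond recipients a way to opt out. The product-related questionnaire (Section 15.5) has separate MAR-CUTIS and Dermabond columns for most questions. Item 9 has neither device, which points to a wording slip and not to a deliberate choice.

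**Step 5: what control-arm data remain.**

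- The Day 0 items and items 8 and 10 of the same form can be answered for either product.
- The product-related questionnaire covers both products, once per site.
- The Month 1 questions on overall experience and recommendation in Section 15.7 are neutral.

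None of these is a per-subject investigator satisfaction rating. The remaining per-subject investigator items cover ease, speed, complications, time, effort, usability and pain. The product-related form has no overall satisfaction rating.

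**Step 6: link to the primary analysis.** None. The primary endpoint is dehiscence until Day 10. Protocol Section 10.1.3.2 makes the secondary efficacy endpoints descriptive.

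**The case against.** A reader might infer that the secondary comparison with Dermabond has no valid control-arm data at all. The documents do not support that: one item is affected, and the sources in step 5 still supply Dermabond data. Protocol Section 6 also supports the subject-comfort objective with the subject-completed questionnaire, and ties investigator overall satisfaction to the product-related questionnaire.

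A reader might also infer that all 63 Dermabond subjects will lack an interpretable answer. That treats a possibility as a certainty. The item begins by referring to this subject, the trial is open-label, and the investigator applied the glue, so many investigators may well answer for the adhesive actually used. What can be said is that the answers would be ambiguous.

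The strongest point on the other side is that responses are recorded in the eCRF, whose wording is not in the documents. Since both the Protocol text and the SAP describe the item neutrally, the product name may survive only in the appendix. This stands as a reason to check the eCRF first. It does not remove the need to correct the printed form, which contradicts the text that describes it.

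The endpoint is also descriptive and exploratory, which limits the consequence. That stands too. It does not make a column that cannot be interpreted worth printing under a label suggesting satisfaction with Dermabond.

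**Conclusion.** The point holds for item 9 alone. As printed, it asks about MAR-CUTIS for every subject, contrary to the neutral descriptions in Protocol Section 9.2 and SAP Section 13.2.6. The by-arm table of this item would not be a sound comparison: up to about 63 Dermabond answers, one third of the planned sample, would be of uncertain meaning.

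The consequence is minor. The item is the form's only satisfaction rating, but it is descriptive, other questionnaire data for the Dermabond arm remain, and the primary noninferiority test is unaffected.

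The conclusion assumes that the form is used as printed or that the eCRF carries the same wording. If the eCRF is already neutral, only the appendix needs correcting.

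**What to change.** 1. Check the eCRF wording of item 9.
2. In Section 15.6, replace the product name in item 9 with 'the study adhesive used in this subject'. Make the same change in the eCRF if it names MAR-CUTIS.
3. Keep the presentation on the Full Analysis Set by randomized group, as SAP Sections 9.4 and 13.2 provide. The wording problem gives no reason to move this item to analysis by treatment received.
4. Add one sentence to SAP Section 13.2.6: Dermabond-arm answers already collected under the MAR-CUTIS wording are flagged and listed separately, and are not tabulated as satisfaction with Dermabond.

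The cost is small but not nil. Changes to the protocol or other study documentation need ethics committee approval (Protocol Section 13.1). If Month 1 forms have already been completed, the data may contain two wordings of the item, and setting the earlier Dermabond answers aside would leave fewer than 63 in that column. Sample size, visits and the primary analysis do not change.
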